8.1.3 Combination with Both Nivolumab and Ipilimumab (Part 3)

The combination of BMS-986205 with nivolumab and ipilimumab in Part 3 will be evaluated in 2 parts, the safety evaluation phase and the cohort expansion phase of the combination in melanoma, NSCLC, and bladder cancer as well as a mixed tumor type cohort.

All safety cohorts will begin with an assessment of safety and tolerability of the triplet combination regimen in a limited number of subjects, including a sentinel subject. As described in [Section 3.1.1.2](#), the NSCLC and melanoma regimen cohorts will begin enrollment first, followed by the bladder regimen cohort once safety and tolerability has been established in either NSCLC or melanoma. Initially, approximately 3 subjects will be treated at the selected dose combination of BMS-986205 with nivolumab and ipilimumab. Due to the potential for early discontinuation, an additional subject(s) may be enrolled to ensure approximately 3 DLT evaluable subjects. Initial safety assessment to allow enrollment in the bladder safety cohort will occur when at least 2 evaluable subjects in either the NSCLC or melanoma safety cohorts have completed a 6-week DLT evaluation period (see [Section 4.5.1](#) for criteria for DLTs). In the melanoma and NSCLC safety evaluation cohorts, if the potential DLT occurring in any third evaluable subject regarding the specific dose combination does not influence the recommendation by BLRM (-Copula) to open enrollment in the bladder safety cohort, then the bladder safety cohort may proceed with enrollment without waiting for the third subject to complete the corresponding DLT observation period. After the initial subjects in each treatment regimen are evaluated, additional increments of approximately 3 to 6 subjects will be treated in the same safety cohort as per BLRM-copula model recommendation that the dose combination is safe. At least 6 DLT-evaluable subjects will be treated and assessed in the selected dosing regimen safety cohort before starting enrollment in the expansion cohort for that tumor type/regimen. Up to 12 DLT-evaluable subjects in total may be treated in the safety evaluation cohort for each tumor type at the dose selected for expansion cohorts for evaluation of safety and pharmacodynamic/PK parameters as required. BLRM (-copula) will be used to monitor the safety of the triplet dose combination on an ongoing basis. If, at any time, the aggregate rate of treatment related toxicities meeting DLT criteria within an individual treatment tumor type/regimen exceeds 33% across all subjects treated in the safety evaluation and dose expansion cohorts, the findings will be discussed and further enrollment may be interrupted. At that time, depending on the nature and grade of the toxicities and after assessing the risk/benefit ratio, a new dose(s) of BMS 986205 for subjects within that dosing regimen may be initiated at a previously tested lower dose level or at a dose level intermediate to previously tested lower dose levels.

Once the initial safety and tolerability has been established independently for each regimen based on safety cohort evaluations, enrollment will begin of subjects into expansion cohorts for further evaluation of safety and tolerability, as well as preliminary evaluation of anti-tumor

efficacy. In the expansion cohorts, BMS 986205 will be administered at a dose determined to be tolerable in combination with each nivolumab and ipilimumab regimen. Each BMS-986205 and nivolumab/ipilimumab combination regimen will be evaluated in tumor-specific cohorts based on the tumor type evaluated in the safety cohorts. The Ipi 1Q8 regimen will also be evaluated in a mixed tumor-type cohorts which may incorporate tumor types evaluated in Part 2 Dose Escalation. This 40 subject cohort is used to obtain preliminary safety, PK, and PD data for the triplet combination in other tumor types.

As all subjects in the melanoma, NSCLC, and bladder disease-specific cohorts will be receiving agents (nivolumab and ipilimumab) with known efficacy, a single-stage design will be utilized for each of these tumor types. Approximately 40 subjects will be enrolled in each of the following cohorts: melanoma PD-L1 positive, melanoma PD-L1 negative, NSCLC PD-L1 positive, NSCLC PD-L1 negative and bladder, mixed tumor type to allow for the exploration of early efficacy signals of BMS-986205 in combination with both nivolumab and ipilimumab in relevant subpopulations. In each NSCLC expansion cohort, approximately 10 subjects will be IO-treatment naïve, 25 will be treatment-naïve, and 5 IO-therapy experienced. In the melanoma cohorts, approximately 35 will be treatment-naïve in the advanced setting and 5 will be IO-therapy experienced in each cohort. In the bladder expansion cohort in Part 3, at least 30 subjects will be IO-therapy naïve.

The anti-tumor activity of the expansion cohorts will be continuously monitored in all subjects who are evaluable for response using the measurements described in [Section 8.3.1](#). In the NSCLC cohort, 16 of 25 responses for the treatment naïve subjects would result in 80% CIs for an ORR that is strictly higher than the historical rate of 45.3%.⁶⁰ In the melanoma cohort, 22 of 35 responses for the treatment naïve subjects would result in 80% CIs for ORRs that are strictly higher than the historical rates of 58.0%.²⁸ In the bladder cohort, 16 of 30 responses would result in 80% CI for ORR that is strictly higher than the historical rate of 38.5%.⁶¹ The CIs are calculated using the Clopper-Pearson method.

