
Once the initial safety and tolerability has been established independently for each regimen based on safety cohort evaluations, enrollment will begin of subjects into expansion cohorts for further evaluation of safety and tolerability, as well as preliminary evaluation of anti-tumor efficacy. In the expansion phase, each BMS-986205 and nivolumab/ipilimumab combination regimen will be evaluated in tumor-specific cohorts based on the tumor type evaluated in the safety cohorts (melanoma, NSCLC, and bladder cancer). The Ipi 1Q8 regimen will also be evaluated in a mixed tumor-type cohorts, which may incorporate tumor types evaluated in Part 2 Dose Expansion. This 40 subject cohort is used to obtain preliminary safety, PK, and PD data for the triplet combination in other tumor types.

As all subjects in the melanoma, NSCLC, and bladder disease-specific cohorts will be receiving agents (nivolumab and ipilimumab) with known efficacy, a single-stage design will be utilized for each of these tumor types. Approximately 40 subjects will be enrolled in each of the following cohorts: melanoma PD-L1 positive, melanoma PD-L1 negative, NSCLC PD-L1 positive, NSCLC PD-L1 negative bladder, and mixed tumor type to allow for the exploration of early efficacy signals of BMS-986205 in combination with both nivolumab and ipilimumab in relevant subpopulations. In each NSCLC expansion cohort, approximately 10 subjects will be IO-treatment naive, 25 will be

treatment-naïve, and 5 IO-therapy experienced. In the melanoma cohorts, approximately 35 will be treatment naïve in the advanced setting and 5 will be IO-therapy experienced in each cohort. In the bladder expansion cohort in Part 3, at least 30 subjects will be IO therapy naïve.

The anti-tumor activity of the expansion cohorts will be continuously monitored in all subjects who are evaluable for response using the measurements described in [Section 8.3.1](#). In the NSCLC cohort, 16 of 25 responses for the treatment naïve subjects would result in 80% CIs for an ORR that is strictly higher than the historical rate of 45.3%.

¹ In the melanoma cohort, 22 of 35 responses for the treatment naïve subjects would result in 80% CIs for ORRs that are strictly higher than the historical rates of 58.0%. ² In the bladder cohort, 16 of 30 responses would result in 80% CI for ORR that is strictly higher than the historical rate of 38.5%. ³ The CIs are calculated using the Clopper-Pearson method.

Endpoints:

Primary Endpoints:

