1.1.5.2 BMS-986205, Nivolumab, and Ipilimumab Combinations

The tumors selected for the evaluation of triplet combination in Part 3 are NSCLC, melanoma, and bladder cancer. Selection was based on evidence of high levels of IDO1 expression (see [Section 1.1.1](#)); the potential to evaluate BMS-986205 with varying doses and schedules of nivolumab and ipilimumab in tumor types with established safety and tolerability profiles for those regimens (see [Section 1.1.6.2](#)); and evidence of increasing clinical benefit with combination immuno-therapy over monotherapy with either agent, described below.

Melanoma

Ipilimumab and nivolumab were both initially evaluated and approved as single agents in metastatic melanoma before being approved in combination.

Ipilimumab was initially approved as monotherapy based on the Phase 3 MDX010-020 study. In this study, compared to melanoma peptide vaccine (gp100), ipilimumab improved OS (10 versus 6 months) and ORR (6 and 11% for ipilimumab-containing arms versus 2% in the gp100 arm).³⁰ Subsequent to this, nivolumab was approved for the treatment of metastatic melanoma based on the CA209037 and CA209066 studies. In CA209037, compared to investigator's choice of chemotherapy, nivolumab administered at 3 mg/kg every 2 weeks improved both objective response (32% versus 11%) and CR rates (3% versus 0%).³¹

The synergistic combination of the 2 agents was evaluated in the CA209067 and CA209069 studies. In both studies, the combination of nivolumab with ipilimumab improved outcomes compared to ipilimumab. In CA209067³², the combination demonstrated a response rate of 58%, numerically higher than either single agent (44% for nivolumab, 19% for ipilimumab). In CA209069, the same combination doses achieved a response rate of 61%, significantly greater than that of ipilimumab alone (11%).³³ PD-L1 status appeared to affect response rates in CA209067, as subjects treated with nivolumab and ipilimumab with PD-L1 positive tumors had a response rate of 72.1% versus 54.8% in PD-L1 negative tumors. Based on those initial results, the combination of nivolumab and ipilimumab was approved as therapy in the first-line treatment of metastatic melanoma and became the first combination immuno-oncology regimen approved in any tumor type.

NSCLC

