1.2 Research Hypothesis

It is anticipated that BMS-986205, administered in combination with nivolumab and in combination with both nivolumab and ipilimumab, will demonstrate adequate safety and tolerability, as well as a favorable benefit/risk profile, to support further clinical testing. No prospective hypotheses are being formally evaluated.

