a) Melanoma, PD-L1 positive

- i) Histologically confirmed, unresectable Stage III or Stage IV melanoma, as specified in the American Joint Committee on Cancer (AJCC) staging system.
- ii) Subjects must be either I-O therapy naïve, or may have received and then had disease progression after 1 prior I-O therapy in the advanced or metastatic setting. For subjects who have received prior immuno-oncology therapy, prior treatment with only 1 agent is permitted; subjects who have received combination I-O therapy are excluded. At least 35 subjects in this cohort will be I-O treatment naïve.
- iii) PD-L1 positive subjects, defined as PD-L1 $\geq 1\%$, are eligible for this cohort. PD-L1 status will be determined using tissue acquired from the mandatory pre-treatment biopsy. Results of previous PD-L1 status testing must be documented if available. (Note: If the PD-L1 status from the pre-treatment biopsy is not available prior to the start of treatment, subjects will be retrospectively assigned to the correct cohort once the result is available.)
- iv) BRAF (V600) mutation status must be known. Both BRAF-mutated and WT subjects are permitted in this cohort

b) Melanoma, PD-L1 negative

- i) Histologically confirmed, unresectable Stage III or Stage IV melanoma, as specified in the American Joint Committee on Cancer (AJCC) staging system.

- ii) Subjects must be either I-O therapy naïve, or may have received and then had disease progression after 1 prior I-O therapy in the advanced or metastatic setting. For subjects who have received prior immuno-oncology therapy, prior treatment with only 1 agent is permitted; subjects who have received combination I-O therapy are excluded. At least 20 subjects in this cohort will be I-O treatment naïve
- iii) PD-L1 negative subjects, defined as PD-L1 <1%, are eligible for this cohort. PD-L1 status will be determined using tissue acquired from the mandatory pre-treatment biopsy. Results of previous PD-L1 status testing must be documented if available. (Note: If the PD-L1 status from the pre-treatment biopsy is not available prior to the start of treatment, subjects will be retrospectively assigned to the correct cohort once the result is available.)
- iv) BRAF (V600) mutation status must be known. Both BRAF-mutated and WT subjects are permitted in this cohort

c) NSCLC PD-L1 positive

- i) Histologically or cytologically confirmed, advanced (ie, unresectable or metastatic) NSCLC of either squamous or non-squamous histology.

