8.4 Analyses

8.4.1 *Demographics and Baseline Characteristics*

Frequency distributions of gender and race will be tabulated. Summary statistics for age, body weight, height, and body mass index will be tabulated.

8.4.2 *Efficacy Analyses*

Listing of tumor measurements will be provided by subject and study day in each arm and dose level. Individual subject's BOR will be listed based on RECIST v1.1 for solid tumors and IWG for blood tumor.

To describe the anti-tumor activity of BMS-986205 in combination with nivolumab and in combination with both nivolumab and ipilimumab, ORR will be calculated. ORR and corresponding 2-sided exact 95% CI by the Clopper and Pearson method will be provided by treatment, and/or dose level and tumor type (if appropriate). Median DoR and corresponding

2-sided 95% CI may be reported by treatment, and/or dose level and tumor type (if appropriate). DoR will be analyzed using the Kaplan-Meier method.

In addition, PFSR, the probability of a subject remaining progression free or surviving to 24 weeks, will be estimated by the Kaplan-Meier methodology, by treatment, tumor type and dose level. The corresponding 90% CI will be derived based on the Greenwood formula.

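### Part 3 melanoma benchmark: 22 of 35 responses does not exclude the 58.0% historical rate at the 80% level; 25 of 35 is the first count that does

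*Combined protocol and SAP*

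**What the plan says.** Section 8.1.3 gives one response benchmark for each Part 3 tumor type and names Clopper-Pearson as the interval method. For melanoma it states that "22 of 35 responses for the treatment naïve subjects would result in 80% CIs for ORRs that are strictly higher than the historical rates"; the rate printed there is 58.0%. The Part 3 sample-size text of the synopsis makes the same claim for the same count: it "would result in 80% CIs for ORRs that are strictly higher than the historical rates of 58.0"%. The companion benchmarks are 16 of 25 against 45.3% for NSCLC and 16 of 30 against 38.5% for bladder.

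The denominator and the rate both have support elsewhere. Section 8.1.3 plans about 35 treatment-naïve subjects in each melanoma cohort. Section 1.1.5.2 reports, for nivolumab plus ipilimumab in melanoma, that "the combination demonstrated a response rate of 58"%.

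On the use of the result, Section 1.2 says "No prospective hypotheses are being formally evaluated", and Section 8.4.2 plans to report ORR with a "2-sided exact 95% CI by the Clopper and Pearson method will be provided by treatment" and, where appropriate, by dose level and tumor type.

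**The concern.** An observed rate of 62.9% in 35 subjects is less than 5 percentage points above 58.0%. An exact 80% interval at this sample size reaches roughly 12 points below the estimate, so it cannot lie wholly above 58.0%. The statement looks false on its face.

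This is the only printed response benchmark for the Part 3 melanoma cohorts. Section 8.3.1 makes anti-tumor activity in Part 3 a co-primary objective, and the benchmark stands in the paragraph of Section 8.1.3 on continuous monitoring of that activity. Someone who uses the printed count during monitoring would take 22, 23 or 24 responders as excluding the historical rate when none of them does.

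**Working it through.** **Inputs** (all from Section 8.1.3): x = 22, n = 35, historical rate 58.0%, confidence level 80%, Clopper-Pearson method.

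**Formula.** Two-sided 80% limits, with 10% in each tail:
- lower = Beta quantile(0.10; x, n − x + 1)
- upper = Beta quantile(0.90; x + 1, n − x)

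**Step 1: does the method reproduce the plan's other 80% statements?** It does.

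| Cohort | x/n | Recomputed lower limit | Plan says |
|---|---|---|---|
| NSCLC, Part 3 | 16/25 | 49.2% | above 45.3% |
| | 15/25 | 45.2% | (fails, so 16 is the minimum) |
| Bladder, Part 3 | 16/30 | 40.1% | above 38.5% |
| | 15/30 | 37.0% | (fails, so 16 is the minimum) |
| Part 2, 35 subjects | 7/35 | 11.5% | 11% |
| Part 2, 27 subjects | 11/27 | 27.7% | 28% |
| Part 2, 37 subjects | 5/37 | 6.7% | 7% |

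**Step 2: melanoma, n = 35, target 58.0%.**

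| Responders | Observed | 80% interval | P(X ≥ x) if true ORR = 58% | Excludes 58.0%? |
|---|---|---|---|---|
| 22 | 62.9% | 50.6% to 73.9% | 34.4% | No |
| 23 | 65.7% | 53.5% to 76.5% | 22.7% | No |
| 24 | 68.6% | 56.5% to 79.0% | 13.6% | No |
| 25 | 71.4% | 59.4% to 81.4% | 7.3% | Yes |

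The tail column is an equivalent check: the lower limit exceeds 58% only when that probability is below 10%.

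**Step 3: could another method be behind the 22?** 80% lower limits for 22/35 are 52.0% (Wilson), 52.1% (Jeffreys) and 52.4% (Wald). A one-sided 80% exact bound is 54.3%. Pooling two cohorts at the same rate (44/70) gives 54.5%. All are below 58.0%.

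**Step 4: for which inputs would 22 be right?** With a rate of 58.0%, 22 is the minimum count only for 30 subjects (22/30 gives 60.3%; 21/30 gives 56.8%) or 31 subjects (22/31 gives 58.1%); at 32 it already fails (56.0%). With 35 subjects, 22 is the minimum only for a historical rate from about 47.8% (the lower limit at 21/35) to just under 50.6% (the lower limit at 22/35).

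**Step 5: comparison across tumor types.** If the true ORR equals the stated historical rate, the chance of reaching the printed count is 4.7% for NSCLC (16/25), 7.1% for bladder (16/30) and 34.4% for melanoma (22/35). At 25/35 the melanoma figure is 7.3%, in line with the other two. These are chances of reaching a benchmark, not design error rates.

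**The case against.** The strongest objection concerns weight. No hypothesis is tested, the cohorts are exploratory, no stopping or expansion rule is attached to the count, and the number 22 enters no planned analysis. This stands and limits the consequence.

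The planned analysis would not be misled by the misprint. The two-sided 95% interval is 44.9% to 78.5% at 22/35 and 50.7% to 83.2% at 24/35, and both contain 58%. It also contains 58% at 25/35 (53.7% to 85.4%). Correcting the count therefore repairs the 80% statement only; it does not make 25 responders exclude 58% in the reported 95% interval.

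It is also fair to say that the documents do not show which of the three numbers is wrong. Section 8.1.3 and Section 1.1.5.2 cite different references for the 58%, and the sentence speaks of rates in the plural but prints one. That 35 and 58% each have support elsewhere points toward the count, but does not settle it. Finally, the 34.4% and 7.3% assume exactly 35 subjects, where the plan says approximately 35.

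None of this makes the printed sentence true.

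**Conclusion.** The concern holds. As printed, the melanoma benchmark is false by more than 7 percentage points: the lower limit at 22/35 is 50.6%, against the 58.0% it is said to exceed. The count that satisfies the statement is 25 of 35. This rests only on the count, denominator, rate, level and method that the plan prints, and on a calculation that reproduces the plan's other 80% intervals.

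The practical effect is confined to anyone who applies the printed count during monitoring. They would be using a benchmark that is met about one time in three when the true response rate is no better than 58%. Formal inference, safety rules and sample size are not affected. It should be corrected, but it does not threaten the study.

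**What to change.** In Section 8.1.3 and in the Part 3 sample-size text of the synopsis, replace 22 of 35 with 25 of 35 if 58.0% and 35 subjects are what was intended. If the rate or the denominator is the wrong one, correct that instead, so that count, denominator and rate agree.

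An optional clarification while the sentence is open: say whether a single 58.0% is meant for both PD-L1 cohorts. Section 1.1.5.2 reports that PD-L1 positive tumors had a "response rate of 72.1% versus 54.8% in PD-L1 negative tumors", without giving the cutoff used. If cohort-specific benchmarks were wanted, the same method gives 30/35 for 72.1% (lower limit 75.1%) and 24/35 for 54.8% (lower limit 56.5%). Nothing in the plan requires this.

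If the count is the error, the cost is one number in two places. Sample size, safety rules and planned analyses do not change; the printed benchmark becomes harder to reach.

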8.2 Populations for Analyses

- 1) All Enrolled Subjects: All subjects who have signed an ICF and are registered into the IVRS.
- 2) All Treated Subjects: All subjects who received at least 1 dose of study drug.
- 3) The PK dataset includes all available concentration-time data from the subjects who received any BMS-986205 or nivolumab or ipilimumab.
- 4) The Immunogenicity dataset consists of all available immunogenicity data from the subjects who receive nivolumab or ipilimumab and have a baseline and at least 1 post-treatment immunogenicity measurement.
- 5) The Biomarker dataset includes all available biomarker data from the subjects who receive any study drug.

Analyses of safety, extent of exposure, biomarkers, PK, efficacy, and pharmacodynamics will be based on all treated subjects.

8.3 Endpoints

8.3.1 Primary Endpoint(s)

- The primary objective of this study is to establish safety, tolerability, and the MTD/MAD/alternate dose. The assessment of safety will be based on the incidence of AEs, SAEs, AEs leading to discontinuation, and deaths. In addition, clinical laboratory test abnormalities will be examined. AEs and laboratory values will be graded according to the NCI CTCAE v4.03.
- The co-primary objective, anti-tumor activity of BMS-986205 in combination with nivolumab in Part 2 (dose expansion) and BMS-986205 in combination with both nivolumab and ipilimumab in Part 3, will be measured by ORR, DoR, and PFSR based on RECIST v1.1 for solid tumors or IWG for blood tumor. For Parts 1 and 2, disease assessment with CT and/or MRI as appropriate will be performed at baseline, end of Cycle 2, and every 8 weeks. For Part 3, in the melanoma cohorts, the first tumor assessment will occur at Week 12 (\pm 1 week); subsequent imaging will be every 8 weeks thereafter during the treatment period; for NSCLC, imaging assessments will occur every 6 weeks during the treatment period; for bladder, imaging assessments will occur every 6 weeks during the treatment period up to 24 weeks, and then occur every 12 weeks thereafter during the treatment period. For all study parts, assessments continue every 12 weeks for the first year after the EOT visit, and then every 6 months thereafter, up to 2 years following the EOT visit until disease progression per RECIST v1.1 or IWG, or until confirmed disease progression for subjects treated beyond progression (defined as an additional 10% or greater increase in tumor burden volume from time of initial progression including all target lesions and new measurable lesions), at the completion of follow-up, or until subjects withdraw from the study.
- Best overall response (BOR) is defined as the best response designation over the study as a whole, recorded between the dates of first dose until the last tumor assessment prior to subsequent therapy. CR or PR determinations included in the BOR assessment must be confirmed by a second scan performed no less than 4 weeks after the criteria for response are first met. For those subjects who have surgical resection, only presurgical tumor assessments will be considered in the determination of BOR.
- ORR is defined as the proportion of all treated subjects whose BOR is either a CR or PR.
- DoR, computed for all treated subjects with a BOR of CR or PR, is defined as the time between the date of first response and the date of disease progression or death, whichever occurs first.
- PFSR at 24 weeks, 1 year, and 2 years: The proportion of treated subjects remaining progression free and surviving at 24 weeks, 1 year, and 2 years if sufficient data are available. The proportion will be calculated by the Kaplan-Meier estimate, which takes into account censored data.

